## 1. INTRODUCTION

Inorganic nitrate supplementation is associated with improvements in vascular and muscular functions. The effects are mediated by an increased generation of nitric oxide which induces vasodilation of resistance vessels and enhanced P:O mitochondrial coupling. We hypothesise that inorganic nitrate supplementation amplify the effects of caloric restriction on metabolic efficiency and determine lowed losses of lean body mass as well as a lower decrease in resting energy expenditure during WL. We aim to conduct a randomized clinical trial to investigate the effects of inorganic nitrate on body composition and energy expenditure during weight loss in obese older subjects. The primary objective is to investigate whether inorganic nitrate + weight loss induces less mobilization of lean body mass compared to weight loss alone. The secondary outcomes include the evaluation of the effects of inorganic nitrate + weight loss on resting energy expenditure, resting blood pressure, hand grip strenght and micro-vascular function.

Thirty-six older (age range: 50-75y), obese (BMI: 25-40kg/m²) overall healthy subjects will be randomized to two 2-week weight loss interventions. The first intervention will include WL + beetroot juice; the second intervention will include WL alone (negative control). Caloric restriction will be individualised to baseline energy requirements to induce a 40% caloric deficit. Subjects will attend the WL clinic every week. Measurements of body composition (BIA), muscular performance (hand grip strenght), vascular function (blood pressure, laser Doppler) and resting energy expenditure (Indirect Calorimetry) will be performed at baseline and at the end of the study (2 weeks). Saliva and urine samples will be collected at baseline and at each visit to monitor compliance. Blood samples will be collected at baseline for measurement of glucose, insulin, C reactive protein, total cholesterol, high density lipoproteins and triglycerides concentrations.

#### 2. BACKGROUND

The world population is rapidly ageing. Between 2000 and 2050, the proportion of the world's population over 60 years of age will double from about 11% to 22% of the total

population. Ageing is associated with reciprocal changes in body composition (i.e., increase in fat mass and decrease in lean body mass) which are one of the factors leading to the increased cardiovascular and metabolic risk in older subjects. Currently, obesity in older aged subjects is on the rise but the evidence on the most effective and safe strategies for the treatment of obesity at this stage of life remains elusive. A major challenge is the loss of lean body mass during weight loss. Moderate weight loss in older obese subjects with diabetes and hypertension is still recommended as a first line of treatment, often prescribed with regular exercise sessions. The latter has been demonstrated to minimize muscle loss and therefore associated with greater improvements in cardio-metabolic functions and long term weight maintenance. However, physical mobility is often an issue in older obese subjects and therefore alternative strategies to reduce lean body mass loss are fundamental in obesity research.

Inorganic nitrate supplementation is linked to an increase generation of NO via a non-enzymatic pathway involving progressive reduction of nitrate into nitrite and NO. Nitric oxide has pleiotropic physiological functions including regulation of vascular tone and mitochondrial energy efficiency. All NOS isoforms (endothelial, neuronal, inducible) are expressed in skeletal muscles and it appears that NO plays a role in muscle mitochondrial biogenesis, glucose uptake, blood flow and muscle repair. The modulation of NO bioavailability can provide a therapeutic strategy to slow muscle loss during old age and prevents sarcopenia. Recent evidence has demonstrated that inorganic nitrate supplementation increases muscle energetic efficiency and performance during structured exercise in both young and older subjects.

## 3. AIM(S) OF STUDY

The aim of the study is to show whether inorganic nitrate supplementation during weight loss in overweight and obese subjects modify weight loss related changes in resting energy expenditure and body composition.

#### 4. OBJECTIVES

The primary objective of the study is:

1. Determine whether weight loss plus inorganic nitrate is associated with lower decrease in resting energy expenditure

Secondary objectives include:

- 1. Determine whether weight loss plus inorganic nitrate determines less loss in lean body in overweight and obese subjects
- 2. Test whether weight loss plus inorganic nitrate is associated with greater reduction in blood pressure and improvements in endothelial function
- 3. Investigate whether weight loss plus inorganic nitrate determine greater improvements in glucose, insulin and lipid levels
- 4. Investigate whether weight loss plus inorganic nitrate is linked to a greater improvement in physical and cognitive function.

#### 5. HYPOTHESIS

## **5b.** Primary Hypotheses

The project is based on the hypothesis that inorganic nitrate will enhance the effects of caloric restriction on endothelial function and improve metabolic and vascular functions. This may be mediated by increased NO production, enhanced muscular mitochondrial function will improve muscle energetics and minimize the production of reactive oxygen species and local inflammation, which in turn will be linked to a decrease in loss of lean body mass following weight loss and reduce the expected reduction in resting energy expenditure. These benefits will be also impacting on other functions such as muscle strength and cognition function.

#### 6. STUDY DESIGN

This is a two-arm, open-label, parallel randomized clinical trial. Subjects will be either randomized to either caloric restriction plus beetroot juice (as a rich source of inorganic nitrate) or caloric restriction alone (control).

## 7. STUDY SETTING/LOCATION

This is a single-centre study conducted at the Nutrition and Dietetics facilities of the Faculty of Medical School of the University Federico II of Naples, Italy.

#### 8. STUDY POPULATION

Study will be conducted in overweight and obese middle-aged and older men and women attending the weight loss clinical facilities of the Nutrition and Dietetics facilities of the Faculty of Medical School of the University Federico II of Naples, Italy. Subjects will attend a first medical assessment visits and if eligible subjects will be invited to enroll the study after being thoroughly explained the aims, objectives and safety of the study by one of the investigators. Subjects will have at least one day to decide whether they wish to enroll in the trial. In total 36 subjects will be recruited (18 per arm).

#### 9. ELIGIBILITY CRITERIA

## Inclusion criteria are:

We aim to recruit 36 male and female older (50 - 75y) overweight and obese subjects (BMI Range: 25-40 kg/m^2) attending an nutrition clinic. Subjects will be non-smokers and weight stable.

Exclusion	on criteria are (reason for exclusion):
	Current participation in other research clinical studies
_ \ \ \ \ \ \ \ \ \ \ \ \ \ \ \ \ \ \ \	Vegetarianism (likely to have very high nitrate intake)
	Weight change more than 3.0kg in the last 2 months (important influence on systemic
metaboli	ism and vascular function).
$\Box$ $A$	Active cancer and any diagnosis of malignant cancer in the last 5 years (systemic effects
on study	outcomes).
	Diagnosis of chronic and acute metabolic and inflammatory conditions interfering with
the study	y outcome (systemic effects on study outcomes). For example flu, Chrohn's Disease,
rheumat	oid arthritis

Previous diagnosis of type 1 or type-2 diabetes treated with insulin (modification of				
regulation of intermediate metabolism). Type 2 diabetic patients treated with diet only or oral				
hypoglycaemic agents will be included in the study.				
☐ Weight loss medications (sibutramine, orlistat, rimonabant) and history of bariatric				
surgery (weight loss related changes in systemic metabolism).				
□ Drugs: corticosteroids, sildenafil, aspirin, NSAIDs, diuretics, antacids, anticoagulants,				
nitrate-derived agents, anti-cholinergic, (all drugs may have either an effect on NO production				
or insulin sensitivity via different mechanisms).				
☐ Subjects on hormonal therapies (oestrogens, thyroxine, progesteron), anti-hypertensive				
(Ca++ channel blockers, ACE inhibitors, beta-blockers,), statins and any other				
antidyslipidaemic agent, and psychiatric drugs (antidepressants, sedatives, antipsychotics) will				
be excluded if dose has been started/changed in the previous three months. (make sure that				
these disorders are under strict control to avoid interference with the study outcomes).				
☐ Haematological disorders including self-reported anaemia, (risk for the participant and				
effects on the study outcomes).				
☐ Major surgical operations interfering with the study outcomes (systemic effects on				
study outcomes).				
☐ Alcohol intake >21 units/week for men and >14 unites/week women				
Blood donations in the previous 3 months.				

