#### Measurement Protocols

**Questionnaires:** Before and after the intervention participants will complete questionnaires on general health and lifestyle (IPAQ). In addition, participants' diet will be assessed using a standardized semi-quantitative food frequency questionnaire (FFQ). Subjects will also be administered a FFQ to evaluate nitrate intake. Cognitive tests (MMSE, TMT A and B) will also be administered at baseline and end of the study.

**Body composition:** Measurements will be performed at baseline and at the end of the 14-day interventions. Body weight, height and waist and upper-arm circumferences will be measured using standardised protocols.

**Resting blood pressure:** At baseline and end of the study resting blood pressure will be measured in triplicate using a manual BP monitor. Before the measurement participants will be invited to rest for at least 15 minutes. An appropriate cuff size will be utilised for the measurement of each subject which will be used for all other measurements of BP.

**Endothelial Function:** All the measurements will be undertaken in a temperature-controlled measurement room ( $\sim$ 23  $\pm$  1  $^{\circ}$ C). Each subject will be invited to lie supine for a 5 min rest period. A laser Doppler device will be used to measure microcirculatory blood flow.

**Hand-grip strength:** Hand-grip strength will be assessed in both arms at baseline and after intervention to measure the maximum isometric strength of the hand and forearm muscles. A lightweight and portable dynamometer will be used. The researcher will follow a specific protocol for the measurement of hand-grip strength (i.e. allowing one practice trial, and then record the best of three attempts with 30 seconds rest between each of these).

**Cognitive tests:** All participants will complete a short battery of cognitive tasks that includes Mini Mental State Examination and the Trail Making Test [TMT Parts A and B].

**Blood tests:** Fasting blood tests will be performed by each participant before and after the intervention.

**Urine and saliva collection:** A spot urine sample will be collected in the morning (not first void) at the beginning and end of the intervention for the measurement of nitrate excretion. Stimulated saliva sample will be collected in 1.5ml eppendorf tubes. Samples will be stored at -20°C until analyses

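### The three-month stable-dose condition in Section 9 leaves out oral hypoglycaemic agents, although change in glucose and insulin is part of secondary objective 3

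*Protocol*

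**What the plan says.** Protocol Section 9 (Eligibility criteria) treats diabetes in its own item. Insulin-treated diabetes is excluded. Then: "Type 2 diabetic patients treated with diet only or oral" "hypoglycaemic agents will be included in the study". Nothing is said about how long the oral agent or its dose must have been in place.

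A later item in the same list sets a stability condition for other drugs. It opens with "Subjects on hormonal therapies (oestrogens, thyroxine, progesteron), anti-hypertensive" agents, continues through statins and any other "antidyslipidaemic agent, and psychiatric drugs (antidepressants, sedatives, antipsychotics) will", and closes with the rule that such patients will "be excluded if dose has been started/changed in the previous three months". The bracketed reason is to make sure that "these disorders are under strict control to avoid interference with the study outcomes".

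Section 4 (Objectives), secondary objective 3, reads: "Investigate whether weight loss plus inorganic nitrate determine greater improvements in glucose, insulin and lipid levels". Section 11, Measurement Protocols, under blood tests, states: "Fasting blood tests will be performed by each participant before and after the intervention". Section 1 (Introduction), however, describes blood sampling for glucose, insulin and lipids at baseline only.

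**The concern.** The protocol's reason for the stability rule is that a recently altered drug can interfere with the outcomes. That reason applies at least as strongly to oral glucose-lowering drugs, which act directly on two of the measurements named in secondary objective 3. The rule protects the lipid part of that objective, through statins and other antidyslipidaemics, but not the glucose and insulin part. As the criteria stand, a patient who started an oral agent the week before the first visit is eligible.

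With 18 participants per arm, one or two people whose glucose is still moving because of a new drug can visibly shift an arm mean or widen its spread. An analysis plan cannot repair an entry criterion after the fact.

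**Working it through.** **1. Is there a gap?** Set the Section 9 items side by side.

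| Drug class | Status in Section 9 | Three-month condition |
|---|---|---|
| Insulin | Excluded | Not applicable |
| Hormonal therapies | Permitted | Yes |
| Anti-hypertensives | Permitted | Yes |
| Statins, other antidyslipidaemics | Permitted | Yes |
| Psychiatric drugs | Permitted | Yes |
| Oral hypoglycaemic agents | Expressly permitted | None |

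Two other criteria might have closed the gap, but neither does. The exclusion of metabolic conditions that interfere with the outcome cannot, because oral-agent users are expressly admitted. The limit of 3.0 kg weight change in two months concerns weight, not drug dose.

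**2. The plan's own figure.** The only calculated figure is the sample size in Section 12a: a difference of 150 kcal/day, SD 150 kcal/day, power 0.80, significance level 0.05, 18 per group. A two-sided t test with these inputs needs 17 per arm (power 0.807) and has power 0.830 at 18. The stated figure is therefore reproduced to within one participant per arm. It concerns resting energy expenditure, and the present point does not depend on it.

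**3. Illustration: one affected participant.** The protocol gives no SD for glucose change, no size of drug effect and no expected number of oral-agent users. Assumed: SD of two-week glucose change s = 0.5 mmol/L, and one participant in one arm of 18 with a drug-driven shift d of 1 to 2 mmol/L.

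- Movement of the arm mean, and so of the contrast: d/18, that is 1/18 = 0.06 and 2/18 = 0.11 mmol/L.
- Standard error of the contrast without the affected participant: 0.5 × √(2/18) = 0.167 mmol/L.
- Movement in standard errors: 0.056/0.167 = 0.33 and 0.111/0.167 = 0.67.
- Variance in the affected arm: 0.25 + (1/18)(17/18)d² = 0.302 for d = 1 and 0.460 for d = 2.
- Pooled SD: √((0.25 + 0.302)/2) = 0.53 (+5%) and √((0.25 + 0.460)/2) = 0.60 (+19%).

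These relative figures depend only on r = d/s. The movement is r/6 standard errors, since (r/18)/√(2/18) = r/6. The pooled SD is multiplied by √(1 + 17r²/648). If s were doubled to 1.0 mmol/L, r would be 1 to 2 instead of 2 to 4. The contrast would then move by 0.17 to 0.33 standard errors and the pooled SD would rise by about 1% to 5%.

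**4. Illustration: a share of participants in both arms.** Suppose a share p of participants has independent extra variation with SD k times the base SD. The SD is multiplied by √(1 + pk²). With 18 per arm, a two-sided t test detects 0.96 SD with 80% power. For that same true difference:

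| p | k | SD multiplier | Power |
|---|---|---|---|
| 5% | 1 | 1.025 | 78% |
| 30% | 1 | 1.140 | 69% |
| 5% | 2 | 1.095 | 73% |
| 30% | 2 | 1.483 | 47% |

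Of 36 participants, 5% is about 2 and 30% about 11. The effect runs from trivial to material, and the protocol gives nothing that places it within this range.

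**5. Is change measured?** Section 11, Measurement Protocols, has fasting blood taken before and after the intervention. Section 1 has it at baseline only. Neither Table 1 nor the visit descriptions in Section 11c mention a blood draw. If blood were taken at baseline only, there would be no change comparison to disturb, and secondary objective 3 could not be assessed at all.

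**The case against.** The strongest reply is that this is a design choice, not an error. Diabetes has its own item, and the authors deliberately admit patients on diet or oral agents. Glucose and insulin appear in a secondary objective, but not in the primary outcome (Section 10a) or the secondary outcome list (Section 10b). Whether follow-up blood is taken is itself unclear. Timing also softens the example: baseline measurements come about seven days after the first visit, so a patient who began a drug the week before that visit is some two weeks into it at baseline, and only further drift over the next 14 days enters the change.

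Much of this stands. It limits the size of the point and makes it conditional on follow-up blood being taken. It does not remove the inconsistency, because the reason that Section 9 gives for its stability rule covers the omitted class, and no reason is given for leaving it out.

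A reader might infer more than the text supports:

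- **That oral hypoglycaemics are the only permitted metabolic class outside the rule.** The rule names certain classes, some of them not metabolic, and any drug not listed anywhere is also admitted without condition. The text supports only that this expressly admitted class is not among those named.
- **That the arm comparison is biased.** Allocation is randomised, so recent drug changes fall on either arm by chance.
- **That the SD rises by 10% to 36%.** On the assumptions of the first illustration, that is the SD of the affected arm alone (√0.302 = 0.55 and √0.460 = 0.68, against 0.50). The comparison uses the pooled SD, which rises by about half as much.

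**Conclusion.** The point holds as a minor one. Section 9 applies a stable-dose condition to four groups of drugs in order to protect the outcomes. It expressly admits users of oral hypoglycaemic agents without that condition, although between-arm change in glucose and insulin belongs to secondary objective 3. The consequence is avoidable variance and possible chance imbalance in a secondary comparison.

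The size is not known. One affected participant moves the contrast by about 0.3 to 0.7 of its standard error and raises the pooled SD by about 5% to 19%, but only under an assumed SD of 0.5 mmol/L and an assumed shift of 1 to 2 mmol/L. A larger SD makes the effect smaller. A reader might also infer that the primary comparison is weakened; nothing in the protocol shows that resting energy expenditure or its sample size is affected. The point also presupposes that blood is taken at the end of the intervention, as Section 11 says and Section 1 does not.

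**What to change.** Reconcile the two items in Section 9, so that the existing started-or-changed entry condition also covers oral hypoglycaemic agents. If the exception is intended, give the reason in one sentence. This concerns who may enter the trial and asks for no change to anyone's treatment.

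In the same revision, settle whether blood is taken at the end of the intervention, align Section 1 with the blood-test paragraph of Section 11, and show the draws in Table 1.

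The cost is one phrase in Section 9, a correction to the sampling text, and a slightly smaller pool of eligible diabetic patients.

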## 10. STUDY OUTCOMES

## 10a. Primary Outcome

The primary outcome of the study is differences in resting energy expenditure and body composition between weight loss plus nitrate compared to weight loss alone after a 2-week weight loss treatment.

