## 12. STATISTICAL CONSIDERATIONS AND DATA ANALYSIS

### 12a. Sample size and statistical power

The sample size calculation was performed using G-Power (version 3). The model selected for the study was a t test model for independent measures. The outcome for the calculation of sample size was difference in REE between intervention and control. A difference between intervention and control of 150 kcal/day (SD:  $\pm 150 \text{kcal/day}$ ). Power and significance levels were set at 0.80 and 0.05, respectively. Using these parameters we estimated a total sample size of 18 participants per group, i.e, 36 participants in total.

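### The protocol ranks resting energy expenditure and lean mass as primary in three conflicting ways, sizes only the former, and gives no rule for success

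*Protocol*

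**What the plan says.** The protocol ranks the same two variables in three ways, all in current text.

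- **Section 1 (Introduction)** puts lean mass first: "The primary objective is to investigate whether inorganic nitrate + weight loss induces less mobilization of lean body mass compared to weight loss alone". It then demotes REE: "The secondary outcomes include the evaluation of the effects of inorganic nitrate + weight loss on resting energy expenditure".
- **Section 4 (Objectives)** gives the reverse order. The primary objective is "Determine whether weight loss plus inorganic nitrate is associated with lower decrease in resting energy expenditure", and the first secondary objective is "Determine whether weight loss plus inorganic nitrate determines less loss in lean body in overweight and obese subjects".
- **Section 10a (Primary Outcome)** promotes both: "The primary outcome of the study is differences in resting energy expenditure and body composition".

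Section 12a sizes the trial on one of them: "The outcome for the calculation of sample size was difference in REE between intervention and control". The inputs are a difference of 150 kcal/day, an SD of 150 kcal/day, power 0.80 and significance level 0.05, giving 18 per group.

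Section 12b plans a time-by-group interaction for the measured outcomes in general. It does not single out a primary test and has no rule for more than one primary endpoint.

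**The concern.** A confirmatory result needs one endpoint, or one stated combination rule, fixed before the data are seen. Here a significant REE result with a null lean-mass result is a success under section 4, a failure under section 1 and undetermined under section 10a. The opposite pattern is a success under section 1 and a failure under section 4.

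The third version adds a further uncertainty, because body composition is not one variable. Section 1 and the visit descriptions in section 11c point to bioelectrical impedance (BIA). The body composition paragraph under Measurement Protocols lists weight, height and circumferences and mentions neither BIA nor lean mass. Body weight can thus be read as part of the primary outcome, while section 10b lists weight loss as secondary.

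At stake are the error rate attached to a positive claim and the endpoint to which the stated power applies. The trial is open-label (section 6), which makes a fixed endpoint more important.

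**Working it through.** **Step 1. Set the sections side by side.**

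| Protocol section | REE | Lean mass / body composition |
|---|---|---|
| 1 Introduction | secondary | primary (lean mass) |
| 4 Objectives | primary | secondary (lean mass) |
| 10a Primary Outcome | primary | primary (body composition, undefined) |
| 12a Sample size | sized | not sized |

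Sections 1 and 4 assign opposite ranks, and section 10a agrees with neither. No section is said to govern.

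**Step 2. Reproduce the stated sample size.** Inputs from section 12a: difference 150, SD 150, so d = 150/150 = 1.0; independent-samples t test; alpha 0.05; power 0.80. Sidedness is not stated; two-sided is assumed.

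- Normal approximation: n per arm = 2 × (1.96 + 0.84)² / d² = 15.7, rounded up to 16.
- Noncentral t, with df = 2n − 2 and noncentrality d × √(n/2): power is 0.781 at n = 16, 0.807 at n = 17 and 0.830 at n = 18 (noncentrality √9 = 3, df = 34). The smallest adequate n is 17.

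The stated 18 per arm is within two of both results, so it reproduces. For REE alone it gives 83.0% power, provided all 18 per arm are analysed.

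**Step 3. Type I error if either endpoint were enough.** Take two tests, REE and lean mass, each at two-sided 0.05.

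- Independent: 1 − 0.95² = 0.0975.
- Correlated test statistics (simulated bivariate normal, 1,000,000 draws):

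| Assumed correlation | P(at least one false positive) |
|---|---|
| 0 | 0.097 |
| 0.3 | 0.095 |
| 0.5 | 0.091 |
| 0.7 | 0.083 |
| 0.9 | 0.070 |

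The protocol gives no correlation, so this is a range. It tends to 0.05 as the correlation approaches 1.

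**Step 4. If both endpoints were required.** The chance of a false overall claim is then at most 0.05, because each test must pass at 0.05. Power becomes the problem. Joint power cannot exceed the 0.830 for REE, and its actual value depends on a lean-mass effect and SD that the protocol does not give. As an illustration only, with d = 1.0 assumed for lean mass as well and independent tests, joint power at 18 per arm is 0.830² = 0.689. Under independence, a joint power of 0.80 would need lean-mass power of 0.80/0.830 = 0.964.

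**Step 5. If REE were the single primary endpoint.** Step 2 applies unchanged: alpha is 0.05, power is 83.0%, and 18 per arm stands.

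**The case against.** The strongest reply is that the intended endpoint can be discerned. The formal objectives and the sample size section both point to REE, and section 1 is only an introductory summary. This stands as evidence of intent and makes the repair mainly editorial. It does not remove the conflict, because section 10a is the formal outcome definition and it departs from section 4. A separate statistical analysis plan could add detail, but the protocol would still contradict itself.

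Three stronger readings are tempting and are not supported.

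- **That the plan declares success on any one endpoint.** No section says so. The conjunction in section 10a can equally mean that both are required, in which case type I error does not inflate. What the text supports is that nothing prevents an either-or claim.
- **That endothelial function is a further competing primary.** Section 5b, headed Primary Hypotheses, does open with the expectation that "inorganic nitrate will enhance the effects of caloric restriction on endothelial function". But it sets out a mechanism and goes on to lean mass and REE. Wherever vascular or endothelial function is ranked (sections 1, 4 and 10b), it is secondary.
- **That three or four primary tests are in play, with correspondingly higher error rates.** That needs an endpoint list which the protocol does not give. The term body composition is loose, but lean mass is the only component that the objectives and hypothesis name. Only the two-endpoint calculation rests on named candidates.

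Splitting alpha at 0.025 each would lower REE power at 18 per arm to 74.1%. The protocol proposes no such split, so this is not a defect of the plan.

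**Conclusion.** The contradiction is real. The protocol has three incompatible statements of its primary endpoint, only REE was sized, and no success rule is given. It needs correcting before the trial can support a confirmatory claim.

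The size of the harm depends on how the gap is filled:

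- **Either endpoint accepted:** type I error of about 8 to 10% against the stated 5%, for an assumed correlation of 0.7 to 0, and less at higher correlation (7.0% at 0.9).
- **Both required:** no inflation, but the 0.80 power is unsupported.
- **REE alone:** the stated error rate and power both hold.

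These figures assume two-sided tests at 0.05, and the power figures also assume complete data on 18 per arm. Inflation is a possibility that the text leaves open, not a rule that it states.

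**What to change.** Name the between-arm difference in REE at 2 weeks as the single primary endpoint, since it is the only one sized and the one that section 4 already puts first. Make BIA lean mass and all other body composition variables secondary. Amend sections 1 and 10a to agree with sections 4 and 12a; section 5b can stay as rationale.

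The change is to wording only. The sample size remains 18 per arm, with about 83% power at the stated difference and SD. The cost is that lean mass loses its primary status.

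If the sponsor wants both endpoints to be primary, the protocol must define the body composition variable, state whether one or both must succeed, give a lean-mass effect and SD, and re-size the trial to match.
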